5.10 SUBJECTS LOST TO FOLLOW-UP

If the Investigator or study coordinator has attempted to contact a subject at least three times within 60 days and received no response, the subject may be considered lost to follow-up. The Investigator or study coordinator will document the minimum of three attempts to contact the subject, including sending a certified letter, and contacting the Sponsor, prior to terminating the subject from the registry.

6.0 REPORTING OF ADVERSE EVENTS AND SERIOUS ADVERSE EVENTS

6.1 DEFINITIONS

An “Adverse Event” (AE) is any clinical finding that is an undesired or pathological change in a registry subject as indicated by signs, symptoms, illnesses and events that develop or worsen in severity in association with the registry whether or not thought to be related to the device or procedure. Adverse events include current illness, injuries, side effects, toxicities, allergic reactions, or events that occur or worsen during the course of a clinical study. This registry will only collect carotid procedure and device related adverse events as well as any carotid related clinical findings.

Adverse Events will be classified as Serious Adverse Events (SAEs) if the event:

- is life threatening (even if temporary in nature) or fatal;
- results in permanent impairment of a body function or permanent damage to a body structure;
- requires medical or surgical intervention to preclude permanent impairment of a body function or permanent damage to a body structure; or
- requires or prolongs hospitalization.

Once a clinical finding is noted, and the finding is classified as an AE or SAE, the relationship to the device will be classified as follows:

- Not Related: The event is due to an underlying or concurrent illness or effect of another device, drug or intervention and is not related to the use of the registry device.

- **Possible:** The event has a strong temporal relationship to the use of the registry device, and an alternative etiology is equally or less likely.
- **Probable:** The event has a strong temporal relationship to the use of the registry device, and another etiology is unlikely or significantly less likely.
- **Definite:** An event that can only be attributed to the use of the registry device.

If a SAE is determined to be probably or definitely related to the device and has not been previously anticipated, the clinical finding would be classified as an unanticipated adverse device effect (UADE). An UADE is defined as “any serious adverse effect on health or safety or any life-threatening problem or death caused by, or associated with, a device, if that effect, problem, or death was not previously identified in nature, severity, or degree of incidence in the investigational plan or application (including a supplementary plan or application), or any other unanticipated serious problem associated with a device that relates to the rights, safety, or welfare of subjects.”

SAEs that are determined to be probably or definitely related to the study device are referred to as device related serious adverse events (DRSAEs).

The protocol definitions for “device failure” and “device malfunction” and “technical observation” are provided below:

- **Device Failure:** A device has failed if it does not perform according to the Instructions for Use or other labeling provided with the device and, as a result, negatively impacts the treatment when used according to this protocol.
- **Device Malfunction:** A device malfunction is an unexpected change to the device that is not contradictory to the labeling and may or may not affect the performance of the device.
- **Technical Observation:** Malfunction or complaint with a medical device that has the potential to, but may or may not, result in a negative clinical consequence to the subject.

Note: A device failure or device malfunction is considered to be a DRSAE if it causes or contributes to a SAE.

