6.2 REPORTING OF ADVERSE EVENTS

Carotid procedure and device related adverse events are to be completed at any point from the time the subject is enrolled to the time of exit from the registry. Adverse events are to include carotid procedure and device related adverse events as well as any carotid related clinical findings.

Registry subjects will be instructed to immediately report to the Investigator any carotid related unusual signs or symptoms. The

Investigator will take whatever means are necessary to treat the subject, should an adverse event occur. First consideration will be given to the welfare of the subject rather than the successful completion of the registry. All subjects experiencing a carotid procedure and/or device related adverse event will be followed until their clinical outcome is determined, if at all possible, or until completion of the last follow-up visit, whichever occurs later.

All carotid procedure and/or device related findings must be recorded on the appropriate CRF in SUGAR COMMUNITY EDITION, electronic data capture system. A description of the finding, including the start date, resolution date, action taken, and the outcome should be provided, along with the Investigator's assessment of the relationship between the finding and the device. Subjects' complaints of any carotid related symptoms that are outside the normal pattern for the illness treated should be considered AEs.

All carotid procedure and/or device related AE's shall be followed until the event is resolved or determined by the Investigator to be stable. The investigational site will provide relevant follow-up information to the Sponsor upon request.

All SAEs and UADEs must be immediately reported to the Sponsor, CorMatrix Cardiovascular, via telephone or e-mail within 24 hours of the Investigator becoming aware of the event. A completed "Serious Adverse Event" form must be faxed or express mailed to the Sponsor within five working days of the event. The minimum required data to be recorded for an SAE includes: date of event, type of event, actions taken, outcome and, if appropriate, causality and possible relationship to the device(s) used in this registry. In the case of a DRSAE, when possible, the device involved in the failure or malfunction is to be made available to the Sponsor for analysis.

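### Do the gaps in the device-relationship grades of section 6.1, and the lack of a grade for the carotid procedure, call for a change?

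*Combined protocol and SAP*

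**What the plan says.** Section 6.1 gives four grades, all for relationship to the device.

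- The lowest grade, **Not Related**, covers an event due to an illness, or one that is the "effect of another device, drug or intervention and is not related to the use of the registry device".
- The second grade, **Possible**, sets two conditions at once: "The event has a strong temporal relationship to the use of the registry device, and an alternative etiology is equally or less likely".
- The third grade, **Probable**, keeps the condition on time and tightens the one on the alternative cause: "The event has a strong temporal relationship to the use of the registry device, and another etiology is unlikely or significantly less likely".
- The top grade, **Definite**, has no condition on time and reads: "An event that can only be attributed to the use of the registry device".

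The same section uses the grades once more: "SAEs that are determined to be probably or definitely related to the study device are referred to as device related serious adverse events", here shortened to DRSAEs. An unanticipated serious event with either of those two grades is classed as an unanticipated adverse device effect (UADE). A separate rule does not use the grade: "A device failure or device malfunction is considered to be a DRSAE if it causes or contributes to a SAE".

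Section 6.2 asks for the investigator's "assessment of the relationship between the finding and the device". It also states that "All SAEs and UADEs must be immediately reported to the Sponsor", within 24 hours of the investigator learning of the event. The outcome in 3.1.1 covers events related to the carotid procedure as well as to the device. Section 11.2 lists the serious events of both kinds and documents their possible relationship to the device.

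**The concern.** A causality scale should give every event exactly one grade. Taken literally, this one does not, in three places, and a fourth relationship is not graded at all.

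1. If another cause is more likely but the patch cannot be ruled out, the event is too weak for Possible and, on a strict reading, too strong for Not Related. There is no lower grade and no default.
2. Possible and Probable both need a close link in time to device use. For a permanent patch this could mean soon after implantation or at any time while the patch is in place. On the first reading, a late recurrent stenosis with mixed causes gets no grade.
3. An alternative that is much less likely is also less likely, so the event meets both Possible and Probable. That boundary decides DRSAE and UADE status.
4. A complication of the endarterectomy can be graded Not Related as the effect of another intervention, and no grade then shows its link to the procedure.

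At stake is consistency between sites: one site could label a late serious event a DRSAE while another leaves it ungraded. In a single-arm registry, attributed events are the only outcome that 3.1.1 names.

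**Working it through.** The plan states no figure on this point, so the check is logical. The four definitions in 6.1 were applied to six states of the alternative cause, with the temporal condition met or not met (6 × 2 = 12 combinations).

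| State of the alternative cause | Temporal condition met | Not met |
|---|---|---|
| A. Device excluded | Not Related | Not Related |
| B. Alternative more likely, device not excluded | none | none |
| C. Equally likely | Possible | none |
| D. Less likely, but not significantly | Possible | none |
| E. Unlikely or significantly less likely | Possible and Probable | none |
| F. Only the device | Definite | Definite |

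**Strict count.** Without a grade: 1 + 4 = 5 of 12. One combination has two grades, and 12 − 5 − 1 = 6 have one.

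**Dependence on how the states are cut.**
- Splitting state E into its two halves gives 7 × 2 = 14 combinations, of which 1 + 5 = 6 have no grade.
- State F with the condition met is counted above as Definite only. Taken as literally as state E, it also meets Possible and Probable, and the count becomes 5 with none, 5 with one, 1 with two and 1 with three.
- The combinations are not weighted by frequency, so 5 of 12 does not measure how many events are affected.

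**Dependence on the reading.**
- *Device use lasts while the patch is in place.* Section 7.1 lists recurrent stenosis and pseudoaneurysm among the risks of using the device, and 6.2 collects events until exit. Both fit this reading. The right-hand column then drops out, leaving 1 of 6 states (B) without a grade.
- *Not Related as the investigator's best causal judgement.* The definition does not say that a device contribution must be excluded. On this reading B is Not Related. Together with the first reading, 0 of 6 states have no grade.
- *Best judgement, but the narrow reading of time.* C, D and E remain without a grade for a late event, 3 of 6.

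**Effect on the DRSAE label.** State B is a choice between Not Related and Possible, and neither makes a serious event a DRSAE. A and F have the same grade in both columns. C and D are Possible or ungraded, so never a DRSAE by this route. Only E can change the label: through the overlap, where a reader would normally take the higher grade, or for a late event under the narrow reading.

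**What does not depend on the grade.**
- Serious events are reported to the sponsor within 24 hours (6.2).
- Carotid related findings are collected whether or not they are attributed to the device (6.1, 6.2).
- Duplex or approved testing is required at every follow-up visit (5.4 to 5.7).
- Sponsor records keep reports of all procedure or device related adverse events, not only DRSAEs (10.4).
- Early termination rests on a judgement of safety concern, not on a grade (10.2).
- The final report summarises all data collected (11.3).

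**Procedure relationship.** The objective in 2.0 concerns device performance. Section 11.2 lists procedure and device related serious events together and plans no separate procedure-related rate. A missing procedure scale therefore removes no planned result.

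**The case for a change.** The strongest case for a change is that the Possible–Probable boundary has consequences. It decides DRSAE status by the grading route and, for unanticipated serious events, UADE status, and 6.2 ties the return of a device for analysis to a DRSAE. The wording overlaps at exactly that boundary, and for a late event it turns on an undefined phrase. Relatedness to the procedure also helps select which serious events 11.2 lists, yet it rests on an ungraded judgement.

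Part of this stands. The phrase is undefined, the overlap is real, and two sites could label the same late event of state E differently. If the sponsor tabulated DRSAEs, that count would carry some rater variation. But the plan ties no named rate to that label, and the serious events in 11.2 are listed one by one with time course and possible relationship, so a reader can see and reclassify a late event.

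Rewording would not clearly do better. Replacing the temporal phrase with a test of plausibility swaps one undefined term for another, and a carotid event near the patch would nearly always pass it. Keeping the present text for Not Related would still leave out an event from trauma or an unknown cause in which the device is excluded. There is also a cost: 10.1 requires the sponsor and the investigator to sign any amendment. Revision A dates from January 2012, so events already graded would have to be regraded or reported under two scales.

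**Conclusion.** No change is needed. The definitions in 6.1 are loosely worded, and investigators and analysts can fill the gap sensibly: device use covers the time the patch is in place, and an event that meets two grades takes the higher. With Not Related as a best causal judgement, all six states then have one grade. On the strict reading of Not Related, the one state left without a grade does not affect DRSAE or UADE status.

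The remaining effect is some variation between sites in labelling late serious events whose alternative cause is unlikely, which is 1 of the 6 states. Its frequency cannot be given, because the documents hold no event rates or onset times. The registry's descriptive results stay sound as written.

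This rests on two assumptions: that sites read device use as 6.2 and 7.1 suggest, and that no analysis outside section 11.2 depends on the grade. The statement that there is no procedure scale is limited to the visible text, since a passage removed directly after 6.2 and the draft case report forms in Attachment 3 could not be checked.

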6.2 REPORTING OF ADVERSE EVENTS

Carotid procedure and device related adverse events are to be completed at any point from the time the subject is enrolled to the time of exit from the registry. Adverse events are to include carotid procedure and device related adverse events as well as any carotid related clinical findings.

Registry subjects will be instructed to immediately report to the Investigator any carotid related unusual signs or symptoms. The

Investigator will take whatever means are necessary to treat the subject, should an adverse event occur. First consideration will be given to the welfare of the subject rather than the successful completion of the registry. All subjects experiencing a carotid procedure and/or device related adverse event will be followed until their clinical outcome is determined, if at all possible, or until completion of the last follow-up visit, whichever occurs later.

All carotid procedure and/or device related findings must be recorded on the appropriate CRF in SUGAR COMMUNITY EDITION, electronic data capture system. A description of the finding, including the start date, resolution date, action taken, and the outcome should be provided, along with the Investigator's assessment of the relationship between the finding and the device. Subjects' complaints of any carotid related symptoms that are outside the normal pattern for the illness treated should be considered AEs.

All carotid procedure and/or device related AE's shall be followed until the event is resolved or determined by the Investigator to be stable. The investigational site will provide relevant follow-up information to the Sponsor upon request.

All SAEs and UADEs must be immediately reported to the Sponsor, CorMatrix Cardiovascular, via telephone or e-mail within 24 hours of the Investigator becoming aware of the event. A completed "Serious Adverse Event" form must be faxed or express mailed to the Sponsor within five working days of the event. The minimum required data to be recorded for an SAE includes: date of event, type of event, actions taken, outcome and, if appropriate, causality and possible relationship to the device(s) used in this registry. In the case of a DRSAE, when possible, the device involved in the failure or malfunction is to be made available to the Sponsor for analysis.

7.0 RISK/BENEFIT ASSESSMENT

7.1 RISKS TO THE SUBJECT

The possible risks associated with the use of the CorMatrix ECM for Carotid Repair for patch angioplasty after CEA are similar to the risks associated with other patch materials for reconstruction or repair of the carotid artery. Risks associated with the use of the CorMatrix ECM for Carotid Repair include:

- Acute or chronic inflammation (Initial application of the CorMatrix ECM may be associated with transient, mild, localized inflammation)
- Allergic reaction
- Bleeding
- Embolization of ECM
- Infection
- Patch dehiscence
- Pseudoaneurysm
- Recurrent stenosis
- Stroke
- Thrombosis
- Vessel occlusion

The known precautions and warnings are listed in the IFU, included as Attachment 2.

7.2 BENEFITS TO THE SUBJECT

The benefits of the CorMatrix ECM for Carotid Repair used for patch angioplasty after CEA have not been established by previous clinical studies.

Subjects participating in this registry may not receive immediate benefit; however, feedback from this registry will provide valuable information that may benefit subjects in the future.

8.0 INVESTIGATOR RESPONSIBILITIES, RECORDS AND REPORTS

8.1 INVESTIGATOR RESPONSIBILITIES

The Investigator is responsible for ensuring that this registry is conducted according to this protocol and that the signed Informed Consent Form is obtained from each subject prior to their inclusion in this registry.

It is the Investigator's responsibility to ensure that all staff assisting with this registry have the appropriate qualifications and are fully instructed on the registry procedures and respect subject confidentiality, as specified in the Investigator Agreement and Financial Disclosure. All participating Investigators are required to sign an Investigator Agreement and Financial Disclosure form prior to their participation.

The Investigator is responsible for ensuring that the conduct of the registry conforms to the IRB requirements and provides all necessary communication with the IRB including, but not limited to, annual study reports and required adverse event notifications.

8.2 INVESTIGATOR RECORDS

Source documentation and standardized Case Report Forms (CRFs) in SUGAR COMMUNITY EDITION, electronic data capture system will be used to collect complete and accurate records of the clinical data from the registry according to the Good Clinical Practices (GCP) requirements.

The Investigator is responsible for collecting and accurately recording the data generated for this registry.

The Investigator is responsible for ensuring the maintenance of complete, accurate and current records including the following materials:

- All correspondence with the Sponsor and the IRB;
- Subject records, including signed Informed Consent Forms for all enrolled subjects, and all supporting source documents (laboratory reports and reports of diagnostic tests, medical records, etc.) and operative records for each subject;
- The representative copy of the IFU provided with the CorMatrix ECM for Carotid Repair utilized in this registry;
- A copy of the approved protocol for this registry and all subsequent revisions to the protocol;
- A description of any protocol deviation(s) and the justification for the deviation(s);
- Copies of carotid procedure or device related adverse events, device failure/malfunction or Medical Device Reports (MDR) submitted; and
- A copy of the approval letter from the respective Investigational Review Board (IRB), with the names of the participating members of the IRB, the approved informed consent (and any subsequent

revisions) and any specific IRB follow-up or reporting requirements to be addressed during the registry.

8.3 INVESTIGATOR REPORT

The Investigator will be responsible for providing the following reports to the Sponsor for this registry:

8.3.1 Serious Adverse Event

Serious Adverse Events are defined in Section 6.1, and the required reporting timeline and appropriate contacts are outlined in Section 6.2. The Investigator is responsible for reporting all events within the designated timeline and for maintaining initial reports and any follow-up reports that may be completed during the registry. All follow-up reports must also be sent to the Sponsor within five working days of the follow-up report being necessary due to new information or a change in the subject's status.

8.3.2 Withdrawal of Approval

If the IRB withdraws the approval to conduct the registry for any reason, the Investigator should notify the Sponsor as soon as possible and no later than five working days after the withdrawal of the approval.

8.3.3 Deviations from the Investigational Plan

The Investigator must notify the Sponsor and the reviewing IRB of any deviation from the Investigational Plan to protect the life or physical well being of a subject in the case of an emergency. This notice must occur as soon as possible, but in no case longer than five working days after the deviation has occurred. Subjects who do not meet the inclusion/exclusion criteria for the registry may not be enrolled as a deviation; any deviations from the enrollment criteria must receive prior approval from the Sponsor and IRB. Subject visits outside of window will not require a five day notification, but should be reported promptly as a deviation.

8.3.4 Use of Information and Publication

It is intended that the results of the registry may be published in the scientific literature and/or presented at scientific meetings (without disclosing the identity of the subjects in the written data or photographs). Results may also be used in submissions to regulatory authorities. Specific information regarding confidential information, and the collaboration and prior review of any planned publication activities (including presentations) is covered in the separate documentation between the Sponsor and Investigator.

9.0 MONITORING

Study monitors qualified by training and experience, will be responsible for monitoring and overseeing the conduct of the registry. The study monitors may evaluate compliance with the protocol, FDA regulations, any specific recommendations made by the site's IRB and the signed Investigator Agreement. Phone contacts and site visits may be conducted to ensure that the protocol is being followed and that any protocol deviations are properly documented. The Investigator will make available to the study monitor for review all Informed Consent Forms, all completed CRFs in SUGAR COMMUNITY EDITION, electronic data capture system, source documentation and other relevant records for all enrolled subjects at the site. It is important that the Investigator and other relevant site personnel are available for consultation with the study monitors during the monitoring visits and that sufficient time is devoted at the site to the monitoring process.

If a deficiency is noted during an on-site visit (or at any other time during the course of the registry), the study monitor is required to discuss the situation with the Investigator and the Sponsor (if required) to secure compliance.

